Veterans will be recruited through the Primary Care Mental Health Integration, General Outpatient Mental Health, and CBT Clinic programs at the Ralph H. Johnson VAMC and local affiliated VA community-based outpatient clinics (e.g., Trident, Goose Creek, and Beaufort), IRB-approved study flyers will be distributed through each clinic/setting. Within these programs, all Veterans reporting symptoms of depression and anxiety meet with a mental health staff member to complete a clinical interview and self-report measures. If Veterans endorse symptoms consistent with a depressive/anxiety disorder, interest in participating in research will be assessed and. if agreeable, the Veteran will be referred to project staff. All referred Veterans will be called by project staff to discuss the project, confirm initial interest, and schedule the initial research assessment. Research assessments may be completed either in-person or via VA-approved telehealth technologies, based upon the preference of the participant. If the Veteran selects telehealth for the initial research assessment, the consent/HIPAA forms, a selfaddress and stamped envelope, and instructions for the telehealth research appointment will be mailed to the Veteran prior to the appointment. The research assessment will be completed with the project staff to first complete consent documentation and then assess inclusion/exclusion criteria (with a targeted sample of 326 VAMC patients), including a semi-structured clinical interview and self-report questionnaires focused on quality of life, social integration, and psychiatric symptoms (described later). Participants who meet inclusion/exclusion criteria will be randomized into a study condition and will be assigned to a project therapist. Because most VAMC patients who meet study criteria likely will present with multiple depressive/anxiety disorders (Brown et al., 2001), principal diagnosis, or the most impairing of the diagnosable disorders, will be used to inform randomization. Principal diagnosis will be determined via diagnostic severity scores in the Anxiety Disorders Interview Schedule-5 (ADIS-5) (Brown, 2014). To balance diagnoses across the two conditions, a stratified random assignment based on principal diagnosis will be used (MDD and PTSD) ([name], 2015). Based on referrals to the PI's CDA, it is expected that at least 45% of the recruited Veterans will have served in OEF/OIF and >50% will be representative of minority groups. During the consent process, staff will explain the purpose of the research, nature of the interventions, potential benefits and risks, the voluntary nature of participation, and the data collection procedures. If the Veteran agreed to consent, they will be asked to sign the consent form. If the consent is completed via telehealth, staff will ask participants to hold up the signed forms to the camera so that the staff may take a screen shot of the signature. These images will be capture on a VA furnished device and stored on the secure VA research network. Participants will then be asked to mail back the completed, signed consent form in the return envelope provided.

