
Eligibility Criteria

Inclusion criteria: 1) participants must be clearly competent to provide informed consent for research participation, 2) participants must meet DSM-5 criteria for either MDD or PTSD, and 3) participants must be 18 -80 years of age. Exclusion criteria involve: 1) recent history (≤ 2 months) of psychiatric hospitalization or a suicide attempt and/or suicidal ideation with acute intent as documented in their medical record or reported during clinical interview, 2) current diagnosis of substance use disorder as documented in their medical record or reported in clinical interview, 3) acute, severe illness or medical condition that likely will require hospitalization and/or otherwise interfere with study procedures as documented in their medical record (e.g., active chemotherapy/radiation treatment for cancer), 4) recent start of new psychiatric medication (< 4 weeks), 5) diagnosis of traumatic brain injury (TBI) in their medical record and/or endorsement of screener questionnaire (McAllister et al., 2016), or 6) diagnosis of schizophrenia, psychotic symptoms, and/or bipolar disorder as documented in their medical record or reported in clinical interview. Additional comorbid psychiatric diagnoses that were not listed as exclusion criteria are permitted as long as they are considered secondary to the principal diagnosis of MDD or PTSD as determined by the diagnostic interview. Of note, if participants request changes to their psychiatric medications at any time during the treatment, a medication consult will be completed with a prescriber in VA Mental Health. Any changes in medications and/or initiation of non-study psychotherapy will be recorded for inclusion in the analyses as a possible covariate. Ineligible Veterans will be referred for non-studyrelated treatments within mental health at the RHJ VAMC.

Procedures

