TBT was developed as a streamlined protocol to address transdiagnostic avoidance via the use of four different types of exposure techniques (situational/in-vivo, physical/interoceptive, thought/imaginal, and [positive] emotional/behavioral activation). From the transdiagnostic avoidance perspective, the four exposure practices are matched to the type(s) of avoidance experienced by patients based upon their cluster of symptoms/disorders. For example, a patient with PTSD would receive situational and imaginal exposures to address their symptoms, whereas a patient with comorbid PTSD and MDD would receive situational, imaginal, and positive emotional exposures. Per protocol, the first six sessions of TBT are designed to educate on, prepare for, and practice the four different types of exposure techniques. The next five sessions are focused on practicing and refining exposure practices as participants work through their lists of avoided situations/sensation/thoughts. The final session reviews treatment progress and relapse prevention strategies.

Although this specific G-TBT protocol has not been tested in Veterans to date, it mirrors the individual protocol tested in multiple Veteran samples as well as the G-TBT protocol tested in civilians that have been shown to be effective across studies.

G-DSTs Control Condition Matching and Assignment

To provide an evidence-based comparison for the G-TBT condition, G-DSTs will be used that are matched to the participant's principal diagnosis ([name] et al., 2018). G-DSTs will include groups for the most common principal diagnoses that have VA-approved protocols and training programs, including PTSD (Cognitive Processing Therapy for PTSD) and MDD (CBT-Depression). Each of these G-DSTs have published manuals for administration and have received extensive support in the literature (Bieling et al., 2006). Participants randomized to a G-DST group will be matched to the G-DST based on the diagnostic severity scores in the ADIS-5.

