The DSMB will have the authority to temporarily or permanently discontinue the trial if it perceives that harm is occurring due to the intervention. The DSMB will meet with the internal DSMC yearly to review adverse event reports, patient complaints if any, and enrollment rates. Data will be provided at these meetings by the investigators on key variables that may indicate harm (e.g., changes in self-report scores). The DSMB biostatistician will evaluate the confidentiality and integrity of the database and the procedures for recording and storing confidential files. The DSMB also will review the elements of the plan to manage emergencies.

Sample Size Determination for Proposed Analyses

For all study outcomes, Veterans will be randomly assigned (1:1) to the G-TBT and G-DST conditions. To reduce potential Type I errors, the primary outcomes of interest for Primary Aim 1 will be patient-reported IIRS, PCL, and DASS depression scores. The power analysis was calculated to be powered at 90% with a Bonferroni-corrected 1-tailed α = .0008 (.025/3 primary outcomes) to detect non-inferiority for G-TBT in comparison to the G-DSTs. Meta-analyses of group CBT for depression (McDermut, Miller, & Brown, 2001) and Group treatment for PTSD (Haagen et al., 2015; Sloan et al., 2013) found effect size estimates ranging from 0.56 (PTSD; Sloan et al., 2013) to 1.03 (depression; McDermut et al., 2001). In Veterans, Haagen et al. (2015) reported a Hedges g of 0.63. Thus, we conducted our power analysis with a conservative expected d of 0.60. Using procedures recommended by Chow, Shao, and Wang (2017) for non-inferiority designs, which utilize the pre-specified non-inferiority margin

(here prespecified as Δ d = 0) and the estimated effect in the active comparison treatment (d = 0.60), we determined that 152 participants (76 per cell) would be needed. However, this does not account for the group clustering effect.

Following Schnurr et al. (2001), we adjusted the sample size to account for potential group effects. Based on the intraclass coefficient (.025) found in the pilot G-TBT trial ([name] et al., 2018), an estimated 174 participants would be needed to adjust for potential clustering effects if groups average 8 participants. We adjusted the sample size upward 37% to adjust for potential discontinuation and 27% based on observed missing data for telehealth assessments, resulting in a final sample size of 326 participants (163 per cell).

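### Prior and ongoing psychotherapy, including the comparator therapies, is not screened, recorded at baseline, stratified or named for analysis, so the trial cannot check whether repeat exposure to CPT or CBT affects the comparison.

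*Combined protocol and SAP*

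**What the plan says.** Eligibility Criteria lists six exclusions. One concerns medication: "recent start of new psychiatric medication (< 4 weeks". None concerns psychotherapy. The section's only provision on outside therapy is: "Any changes in medications and/or initiation of non-study psychotherapy will be recorded for inclusion in the analyses as a possible covariate". It covers new starts only, and covariate use is left open.

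Recruitment Strategy and Feasibility of Recruitment names the sources as "Primary Care Mental Health Integration, General Outpatient Mental Health, and CBT Clinic programs" at the medical center and its affiliated clinics. G-DSTs Control Condition Matching and Assignment describes the comparator groups as "including PTSD (Cognitive Processing Therapy for PTSD) and MDD (CBT-Depression", chosen because the VA already has approved protocols and training for them. Group Transdiagnostic Behavior Therapy says "this specific G-TBT protocol has not been tested in Veterans to date", and the same sentence adds that it mirrors an individual protocol already tested in several Veteran samples.

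No other section fills the gap:
- Randomization Procedures stratifies by principal diagnosis only.
- The list of instruments contains no treatment-history measure.
- Preliminary Descriptive Analyses covers demographic, quality-of-life, social integration and symptom variables.
- The example covariates in Non-Inferiority Analyses do not include therapy history.

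**The concern.** A Veteran who is still symptomatic after CPT or CBT-Depression is eligible and can be randomised to receive the same therapy again in a group. If randomised to G-TBT, the same Veteran may receive something different. Randomisation makes the history equally frequent in both arms, but it does not make its effect equal if the history modifies response to one arm's treatment more than the other's.

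If repeat courses work less well, the comparator's effect in this sample falls below the planning value of 0.60, and an observed G-TBT advantage could partly reflect repeat exposure. The margin is d = 0 and the claim requires a confidence interval that excludes 0, so there is no tolerance to absorb such a shift. Without baseline data on therapy history, the trial has no planned way to examine this.

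**Working it through.** **1. The plan's own sample size.** Inputs from Sample Size Determination: d = 0.60, SD = 1, power 90%, one-sided alpha .025/3 = .0083.

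n per arm = 2(z_alpha + z_beta)² / d² = 2(2.394 + 1.282)² / 0.36 = 75.1, rounded up to 76, or 152 in total. This matches the plan. The printed alpha of .0008 gives 110 per arm (220 in total) and does not. I therefore use .0083, and the two figures need to be reconciled in the plan.

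Clustering: 1 + (8 − 1) × .025 = 1.175, and 152 × 1.175 = 178.6 against the stated 174 (within 3%). Final size: 174 × 1.37 / 0.73 = 326.5 against 326.

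**2. Size of a possible shift.** The documents give no rate of prior CPT or CBT, no response history and no repeat-course effect, so the following are assumptions:
- f: share of Veterans previously exposed to their matched G-DST (equal in both arms by randomisation)
- r: share of the 0.60 comparator effect lost on repetition
- k: G-TBT's loss as a fraction of the comparator's loss

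Shift toward G-TBT = 0.60 × f × r × (1 − k).

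**3. Effect on the decision.** Suppose the arms are truly equal in unexposed Veterans. Then the probability of a claim per outcome = 1 − Φ(2.394 − shift/SE), with SE = √(2/n):
- n = 76 (the plan's number before inflation): SE = 0.162
- n = 163/1.175 = 138.7 (clustering allowed for, no attrition): SE = 0.120

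| f | r | k | Shift (SD) | n = 76 | n = 138.7 |
|---|---|---|---|---|---|
| any | any | 1 | 0 | .0083 | .0083 |
| .10 | .25 | 0 | 0.015 | .011 | .012 |
| .25 | .50 | 0.5 | 0.0375 | .015 | .019 |
| .25 | .50 | 0 | 0.075 | .027 | .038 |
| .50 | .50 | 0.5 | 0.075 | .027 | .038 |
| .50 | .50 | 0 | 0.15 | .071 | .126 |

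At the printed alpha of .0008, the 0.15 shift gives .013 and .028.

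**4. Ongoing outside therapy.** If it runs in both arms, it tends to pull the true difference toward 0. Under a rule that needs the interval to exclude 0, this lowers the chance of a claim when G-TBT is better and cannot lift the false-claim rate above the nominal level when the arms are equal.

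**The case against.** A reader might infer that prior exposure falls on the comparator and therefore biases the trial toward G-TBT. The documents do not support that.

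- Exposure is spread over both arms. A shift needs a history-by-arm interaction that no section states or quantifies.
- Prior exposure to individual TBT is possible too and is not screened either. G-TBT's content, "four different types of exposure techniques (situational/in-vivo, physical/interoceptive, thought/imaginal, and [positive] emotional/behavioral activation", includes behavioral activation, so it may not be wholly new to a Veteran who has had CBT.
- The recruitment section describes referral after a symptom interview, including from primary care. A recruit need not have had any CBT.
- Whether the trials behind the 0.60 already enrolled previously treated patients cannot be checked from these documents.
- Enrolling treatment-experienced Veterans is a defensible choice for a VA comparison. For that population, a poorer result on repeating a therapy is part of the real difference. The claim rates above are false only with respect to Veterans not yet exposed.

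A second tempting inference is that outside therapy makes non-inferiority easier to show by bringing the arms together. That applies to a trial with a tolerance margin, not to one with a margin of 0.

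All of this limits the claim about direction and size. The gap in the data remains. Charts could be searched later, but only as a post hoc exercise without prespecified definitions.

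**Conclusion.** The omission is established: therapy history is not screened, recorded at baseline, stratified or named for analysis, and only new non-study therapy is captured. A bias toward G-TBT is possible but not shown. It requires that earlier non-responders are common and that they gain less from repeating CPT or CBT than from G-TBT.

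Under the assumptions above, the shift lies between 0 (both arms lose equally) and about 0.15 SD (half exposed, half the effect lost, G-TBT unaffected). These values illustrate and are not estimates or bounds. The larger sample-size column ignores attrition, so it is the upper of the two rates. Ongoing outside therapy works against a G-TBT claim. The point is a low-cost improvement to data collection and analysis, not a demonstrated flaw in the result.

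**What to change.** At the eligibility record review and interview already planned, record:
- (a) any prior course of CPT, CBT-Depression or TBT, with response if documented
- (b) psychotherapy for MDD or PTSD ongoing at entry

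Include both as baseline covariates in the primary model. Main-effect adjustment does not remove an interaction, so also prespecify the condition-by-prior-exposure contrast. Exposure to the matched G-DST can be defined in both arms, because principal diagnosis is set before randomisation. Report the three primary d's with confidence intervals in Veterans who have not had their matched G-DST, as a sensitivity analysis and not as an added success criterion. Separately, reconcile the printed alpha of .0008 with .025/3 = .0083.

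The cost is two baseline fields and analysis-plan wording, with no extra visits or participants. The subgroup estimate will be less precise. With half exposed, 76 per arm leaves 38, and its SE rises from √(2/76) = 0.162 to √(2/38) = 0.229. The interaction contrast then has SE √2 × 0.229 = 0.324, against a difference of 0.60 × 0.50 = 0.30 in the largest case above. It should therefore be read as an estimate with its interval, not as a test. No change to eligibility or treatment is proposed.

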The full intent-to-treat (ITT) analysis set will comprise all randomized participants. Missing data in the full analysis set will occur if participants discontinue treatment prior to the end of the study or do not complete an outcome measure. Participants will not be discontinued from the study because of non-adherence and all will remain in the study unless consent is withdrawn or if there are concerns regarding participant safety. Missing data for the ITT analysis set will be imputed using multiple imputation (MI) methods, which are superior to most alternative missing data approaches even when data is missing completely at random (MCAR) or missing at random (MAR; Schafer & Graham, 2002; Enders, 2010). Although the use of MI will result in the least biased parameters, regardless of data missingness, several approaches will be undertaken to better understand the exact mechanisms for missing data. Little's (1988) MCAR test will be applied to all final models to determine whether data can be considered MCAR. Further, the results of analyses using study completers and protocol adherers (completer and per-protocol analyses) will be compared with results using the ITT analysis set to test sensitivity of study conclusions to study discontinuations and protocol non-adherence. Baseline differences also will be explored between treatment completers and those that discontinue. If baseline differences are detected, these covariates will then be included in the final model as auxiliary variables to improve the plausibility of assuming data is MAR (Collins et al., 2001; Enders, 2010; Graham, 2003;). Finally, discontinuation proportion will be used as one of the outcome measures of intervention feasibility.

Non-Inferiority Analyses (Primary Aim 1)

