The continuous measures of quality of life, psychological well-being, and social reintegration are CHART (disability), CRIS and CHART (social reintegration), IIRS and V/SF-36 (quality of life and impairment), APPQ (agoraphobia, social anxiety, and interoceptive avoidance), DASS (depression, anxiety, and stress), ADIS-5 (disorder dimensional severity scales), PCL-5 (PTSD), and STICSA-Trait (cognitive and somatic anxiety). Although multiple variables will be examined, the primary outcomes of interest will be IIRS, PCL-5, and DASS depression scores. All other analyses will be conducted in an exploratory fashion to inform future studies. Parameter estimates to calculate the effect size difference will be arrived at using three-level (measurement occasions nested within participants nested within assigned treatment group) generalized mixed-effects regression models (MRM). MRM is a method of repeated measures analyses that allows for modeling of continuous and categorical independent and dependent variables and for appropriate modeling of covariance structures when observations are correlated across time and/or across group. This analytic approach fully captures variability in outcomes across multiple follow-up assessments and accounts for any potential effect of the group to which a participant is assigned and is thus preferred over methods that collapse data over time. We will calculate between-group treatment differences as the d, based on the effect of treatment condition on the intercept parameter when the model is centered on post-intervention and on the effect of treatment condition on the intercept parameter when the model is centered on month 6. We prespecified the non-inferiority margin (d) to be 0 (indicating we expected G-TBT to be at least equivalent to G-DST) and the one-sided CI for our three primary analyses at $\alpha = .0008$. In the primary analyses of outcome variables, we will covary for the baseline value of the variable of interest. We will also include the linear effect of time as well as a time by condition interaction effect to determine whether treatment differences (or lack thereof) were stable from post-intervention through the follow-up. Additional covariates (e.g. age, number of psychiatric comorbidities, race, sex, combat theatre, and number of treatment sessions) will be added to the model to adjust for putative confounding variables. Effect size CIs that do not contain 0 provide evidence in support of noninferiority for G-TBT.

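### Medication changes and non-study psychotherapy begun after randomisation are left open as covariates, and adjusting for them can shrink a true between-arm difference in either direction

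*Combined protocol and SAP*

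**What the plan says.** Under Eligibility Criteria, the plan provides a consult with a prescriber "if participants request changes to their psychiatric medications at any time during the treatment". It then states: "Any changes in medications and/or initiation of non-study psychotherapy will be recorded for inclusion in the analyses as a possible covariate". It does not say which analyses are meant or what would decide inclusion.

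Under Non-Inferiority Analyses (Primary Aim 1), one covariate is fixed: "In the primary analyses of outcome variables, we will covary for the baseline value of the variable of interest". The section continues: "Additional covariates (e.g. age, number of psychiatric comorbidities, race, sex, combat theatre, and number of treatment sessions) will be added to the model", and gives the purpose as "to adjust for putative confounding variables". Medication change and outside psychotherapy are not in that list. The list is only illustrative, however, and one of its members, the session count, is itself known only after randomisation.

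Under Missing Data: "The full intent-to-treat (ITT) analysis set will comprise all randomized participants". Randomization Procedures makes the same commitment. The completer and per-protocol comparisons deal with discontinuation and non-adherence, not with added treatment. The decision rule is "Effect size CIs that do not contain 0 provide evidence in support of noninferiority for G-TBT", with a margin of d = 0, applied at post-intervention and at month 6.

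**The concern.** A baseline covariate cannot be changed by the assigned therapy. Starting a new medication or outside psychotherapy can be, because participants who remain symptomatic have more reason to seek further help. Such an event is then a consequence of treatment and not a confounder. Conditioning on it compares participants in the two arms who did equally badly, or equally well, by that criterion, and so removes part of the effect that randomisation was meant to reveal. It also does not recover the effect that would be seen without added treatment, because the post-randomisation severity that prompted the start is not controlled.

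The size of the between-arm difference at both time points is at stake, and so is the power of the test. The wording also leaves an analyst free to decide on inclusion once the results are known, which is undesirable in a confirmatory comparison.

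**Working it through.** **Plan's own figure.** The concern disputes no printed number, but the power check needs an alpha and a sample size. With d = 0.60, margin 0, 90% power and one-sided alpha .025/3 = .00833, n per arm = 2 × (2.394 + 1.282)² / 0.60² = 75.1, so 76 per arm and 152 in total, as stated in Sample Size Determination. The printed alpha of .0008 would need 110 per arm, so .025/3 is used here. The plan's figure after clustering is 174; 152 × (1 + 7 × .025) gives 178.6, which is close. The power check uses 174.

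**Size of the distortion.** All inputs here are assumed. There were 2,000,000 simulated participants; higher scores are worse; A = 1 for G-TBT; B is baseline.

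- Outcome without added treatment: Y0 = 0.5·B + δ·A + √0.75·e
- Chance of starting added treatment (R): 1/(1 + exp(−(−1.5 + s·Y0))), with s = 0.75 (weak link) or 1.5 (strong link)
- Observed outcome: Y = Y0 − b·R, with b the benefit of added treatment
- Linear regression of Y on A and B, without R and then with R

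Start rates came out at 21–25% on G-DST and 24–40% on G-TBT. Estimated G-TBT deficit, without R → with R (share lost):

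| Link s | Benefit b | δ = 0.30 | δ = 0.60 |
|---|---|---|---|
| 0.75 | 0 | 0.299 → 0.281 (6%) | 0.602 → 0.563 (6%) |
| 0.75 | 0.3 | 0.291 → 0.283 (3%) | 0.577 → 0.560 (3%) |
| 0.75 | 0.6 | 0.280 → 0.283 (−1%) | 0.555 → 0.561 (−1%) |
| 1.5 | 0 | 0.298 → 0.240 (19%) | 0.600 → 0.478 (20%) |
| 1.5 | 0.3 | 0.280 → 0.242 (14%) | 0.557 → 0.476 (15%) |
| 1.5 | 0.6 | 0.262 → 0.244 (7%) | 0.517 → 0.479 (7%) |

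The shift is approximately the coefficient of R times the arm difference in start rates. For δ = 0.30, s = 1.5, b = 0 this is 0.87 × (0.32 − 0.25) = 0.061, against 0.298 − 0.240 = 0.058. For δ = 0.60, s = 0.75, b = 0.6 the coefficient is −0.08, giving −0.08 × (0.28 − 0.21) = −0.006, which is the slight reversal. In every row the adjusted estimate lies below δ, so adjustment does not recover the effect without added treatment. With δ = 0, all estimates lay within ±0.002 with or without R.

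**A second assumed model.** Starting depends on mid-course severity S = 0.5·B + noise + 0.3·A; the chance of starting is logistic(−1.4 + k·S); Y = 0.8·S + N(0, 0.6²) − b·R. With b = 0 the true deficit is 0.8 × 0.3 = 0.24.

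- k = 1.0: 0.241 → 0.214 (11%) with b = 0; 0.224 → 0.213 (5%) with b = 0.3
- k = 1.5: 0.240 → 0.192 (20%) with b = 0; 0.220 → 0.193 (12%) with b = 0.3
- k = 0.5: 0.240 → 0.233 (3%) with b = 0; 0.231 → 0.231 (0%) with b = 0.3

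With G-TBT set truly better, the advantage shrank by 4–18% under k = 1.0 or 1.5.

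**Effect on the decision.** The same second model was used with b = 0, k = 1.0 and 1.5, 174 analysed, one-sided alpha .025/3 and no clustering. Support was read as an interval wholly on G-TBT's favourable side of 0.

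| Truth for G-TBT (severity scale) | Declared without R | Declared with R |
|---|---|---|
| 0.3 SD worse | 0 of 20,000 | 0 of 20,000 |
| No difference | 0.9% | 0.9–1.0% |
| 0.3 SD better | 24–25% | 18–21% |
| 0.6 SD better | 84–85% | 71–78% |

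**The case against.** The strongest reply is that the plan never commits to this adjustment. The text calls these events a possible covariate, the primary analysis fixes only the baseline value, and the list of additional covariates does not name them. All randomised participants are analysed, nobody is removed for non-adherence, and no text discards outcomes after added treatment, so using outcomes regardless of it is largely the implied default. This stands: a reader might infer that the adjustment is planned, and the documents do not support that. They do leave it permitted, with no rule for deciding.

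A reader might also infer that the adjustment makes a false non-inferiority claim more likely. That reasoning suits a margin that tolerates some deficit. Here the margin is d = 0, and shrinking a deficit leaves it a deficit. In the check, adjustment added no bias at the null and left the declaration rate there practically unchanged; its main cost was power. The exception is a route from arm to added treatment that bypasses severity. If start rates differed by 0.07 for such a reason and the coefficient of R were 0.88 (its value in the strong-link null run with b = 0), a null estimate would move by about 0.88 × 0.07 = 0.06 in favour of the arm with more starters. The documents give no reason to expect this.

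Finally, the unadjusted comparison is itself diluted when added treatment works: a deficit of 0.60 is estimated at 0.517 with b = 0.6 and a strong link. This stands too. It means the unadjusted model answers a different question, the effect regardless of added treatment; it does not make the adjusted model right.

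**Conclusion.** The concern holds in a limited form. The plan earmarks consequences of treatment as possible adjustment variables, and its covariate list does not exclude them. Under assumed inputs in which starting depends on severity, adjustment shrinks a true difference, for or against G-TBT, by 0 to about 20%. The effect is close to nil when the link is weak, and slightly reversed (about 1%) when the link is weak and added treatment works strongly. With the d = 0 margin the consequences are lost power and an understated G-TBT deficit. Inflated false non-inferiority claims are not among them unless arm influences added treatment other than through severity. The documents give no start rates, arm imbalance or dependence on severity, so none of these sizes is a prediction for this trial. The freedom to decide on inclusion after seeing results does not depend on those assumptions.

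**What to change.** In Eligibility Criteria, replace the closing words on inclusion as a possible covariate, and repeat the rule under Non-Inferiority Analyses. Suggested content:

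- Medication changes and non-study psychotherapy begun after randomisation are not covariates in the primary between-arm outcome models.
- All observed outcomes are used regardless of these events, consistent with the intent-to-treat commitments in Randomization Procedures and Missing Data.
- Their frequency, type and timing are reported by arm. It would help to state that recording runs through the 6-month assessment.
- Any analysis that accounts for added treatment is prespecified and labelled as a sensitivity analysis.

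The method for that sensitivity analysis can be left to the sponsor's statistician. Setting outcomes after added treatment to missing and imputing them is one option, but it adds missingness to a trial already planning for 37% discontinuation and 27% missing telehealth assessments.

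The cost is a few sentences, since the events are already to be recorded, and no clinical rule changes. The downside is that the primary estimate includes the effect of outside treatment, which the report should say plainly.

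### A Holm step-down test on the three primary outcomes would gain power over the planned single-step Bonferroni at the same family-wise one-sided .025: a cheap improvement, not an error

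*Combined protocol and SAP*

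**What the plan says.** The combined protocol and SAP names three primary outcomes for Primary Aim 1: "the primary outcomes of interest will be IIRS, PCL-5, and DASS depression scores". Under Sample Size Determination for Proposed Analyses the plan states: "The power analysis was calculated to be powered at 90% with a Bonferroni-corrected 1-tailed" alpha, and the level is given as "Bonferroni-corrected 1-tailed α = .0008 (.025/3 primary outcomes". The inputs are stated there: "we conducted our power analysis with a conservative expected d of 0.60", and a margin "here prespecified as Δ d = 0". The result is 76 per cell before the adjustments for clustering, discontinuation and missing assessments.

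Under Non-Inferiority Analyses (Primary Aim 1) the plan fixes "the one-sided CI for our three primary analyses at" the same printed level, .0008. The section closes by taking an effect-size interval that excludes 0 as evidence of non-inferiority. Each outcome is estimated twice, with the model centred on post-intervention and then on month 6. No step-down, hierarchical or gatekeeping order appears anywhere, and the plan does not say whether success means one outcome or all three.

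**The concern.** Single-step Bonferroni holds every outcome to the smallest share of alpha, even after another outcome has already succeeded. Holm compares the smallest of the three p-values with .025/3, the next with .025/2 and the last with .025, and stops at the first failure. It controls the same family-wise error whatever the correlation, and it rejects everything that Bonferroni rejects.

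What is at stake is the second and third claims. A true effect on, say, the PCL-5 with a one-sided p of .010 fails under the plan, even when the IIRS has cleared .0083. Under Holm it would pass as the second-ranked p-value, because .010 is below .0125.

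**Working it through.** **Inputs from the documents.** Family-wise one-sided alpha .025; three outcomes; power 90%; d = 0.60 in SD units; margin 0; 1:1 allocation. The correlation between the outcomes is not given, so I assume .3, .5 and .7.

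**1. The plan's own figure.** n per arm = 2(z₁₋α + z₁₋β)²/d².
- At α = .025/3 = .00833: 2(2.394 + 1.282)²/0.36 = 75.05, rounded up to 76. This matches the plan.
- At the printed α = .0008: 2(3.156 + 1.282)²/0.36 = 109.4, rounded up to 110. This does not match.
- Power at 76 per arm: the mean of z is 0.60 × √(76/2) = 3.699. Power is Φ(3.699 − 2.394) = 90.4% at .00833, and Φ(3.699 − 3.156) = 70.6% at .0008.

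The trial was therefore sized at .0083, and I use that level below.

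**2. Holm critical values.** .025/3 → 2.394; .025/2 → 2.241; .025 → 1.960.

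**3. Power when all three effects are real.** I simulated trivariate normal test statistics with mean 2.394 + 1.282 = 3.676, so that each outcome has exactly 90% power at .025/3. Clustering is not modelled separately.

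| Assumed correlation | Per outcome, Bonferroni → Holm | All three, Bonferroni → Holm | At least one, both rules |
|---|---|---|---|
| .3 | 90.0% → 94.7% | 76% → 88% | 99.3% |
| .5 | 90.0% → 94.2% | 78% → 89% | 98.4% |
| .7 | 90.0% → 93.7% | 81% → 90% | 97.0% |

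No Bonferroni rejection was lost under Holm in any draw. At 76 per arm (90.4% per outcome) every figure is at most about one point higher. The gain shrinks as the correlation rises: about 12, 11 and 9 points for all three. At correlation .9 and 76 per arm it is 85.6% → 92.0% for all three, and 90.4% → 93.2% per outcome.

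**4. Error.**
- All three null, correlation .5: family-wise error is .022 under both rules.
- Two real effects and one null, correlation .5: error on the null outcome is .008 under Bonferroni and .025 under Holm, which is the family-wise limit.

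**5. Only one real effect** (76 per arm, correlation .5). Power for that outcome is 90.4% under both rules, so Holm adds nothing.

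**The case against.** The strongest reply is that nothing is broken. Bonferroni is valid, the sample size already pays for it, and each outcome meets the 90% target under the plan's own rule. The chance of at least one success is the same either way. All of this stands, so Holm is an efficiency gain and not a correction.

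Three further objections also stand in part.

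- **Error control.** A reader might infer that Holm costs nothing in error. That is true of the family-wise rate only. The error on a lone null outcome, when the other two effects are real, roughly triples, though it stays within .025.
- **Fit with the interval rule.** The plan decides by confidence interval, and Bonferroni bounds match that decision exactly. Under Holm, the second or third outcome could be declared non-inferior while its .025/3 bound still crosses 0. The closing sentence of the non-inferiority section would then contradict the decision unless it is amended.
- **Undefined inputs.** Two time points and three outcomes make six estimates, and the plan does not say which are confirmatory. Ordering three p-values has no meaning until one time point is named. If success required all three outcomes, no alpha split would be needed at all. The plan does not say that it does, and dividing by three suggests separate claims.

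A reader might also infer that correlation between these patient-reported scales is the reason to switch. The figures point the other way, because the gain is smaller at higher correlation.

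**Conclusion.** This is a cheap improvement. Holm gives about 4 to 5 points more power per outcome and about 9 to 12 points more for all three, at the same family-wise one-sided .025 and with no added patients. The size of the gain rests on assumed correlations of .3 to .7 and on a true between-arm difference of d = 0.60 on all three outcomes. That Holm never rejects less than Bonferroni rests on neither.

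Two stronger readings are not supported. The first is that the plan's multiplicity control is wrong or leaves the trial short of power. At .0083 it does neither. The printed .0008 is a separate slip, worth about 20 points of power per outcome at 76 per arm (90.4% against 70.6%), and Holm does not repair it. At the family-wise level that it implies, 3 × .0008 = .0024, Holm reaches only about 75–78% per outcome at 76 per arm (correlations 0 to .9).

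The second is that Holm would make the design robust. The plan describes 0.60 as the estimated effect in the comparison treatment, yet with a margin of 0 the formula uses it as the true advantage of G-TBT. If the two treatments are equal, the chance of success per outcome is about .008 under Bonferroni and about .009 to .010 under Holm at these correlations.

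**What to change.** Before unblinded analysis, amend Non-Inferiority Analyses (Primary Aim 1) as follows.

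1. Name one confirmatory time point, either post-intervention or month 6. State that the three one-sided p-values at that point, against the stated margin, are ordered and compared with .025/3, .025/2 and .025, stopping at the first failure.
2. Amend the closing sentence on intervals that exclude 0, so that the Holm decision governs and the .025/3 bounds are reported as simultaneous intervals for estimation.
3. Use .025/3 = .0083 in place of .0008, here and in the sample size section. This correction is needed whether or not Holm is adopted.

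Leave the sample size unchanged. The cost is a few sentences and no patients. Both downsides should be stated openly: the decision on the second and third outcomes may not match the reported simultaneous bound, so both must be shown; and the error on a single null outcome can rise from about .008 to at most .025.
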